Official Title: Bronx Mindfulness-Based Cognitive Therapy for Migraine Trial

NCT number: NCT02443519

Document Date: 1/3/2019

1) Objective

The current phase 2b study aimed to evaluate the efficacy of Mindfulness-Based Cognitive Therapy for Migraine (MBCT-M) to reduce migraine-related disability in people with migraine compared to wait list/treatment as usual (WL/TAU).

2) Study Design

This is a randomized clinical trial (RCT) testing an 8-week, MBCT-M intervention (involving 8 weekly, 75-90 minute individual sessions) vs waitlist/treatment as usual (WL/TAU) in people with migraine (N=60), with follow-up assessments at 1 and 6 months post-treatment (the latter will be for the treatment group only). This is a Phase IIb trial (ORBIT Model).

3) Study Population

We recruited 60 participants, and randomized 31 participants to MBCT-M and 29 to WL/TAU. Recruitment and randomization was stratified by episodic migraine (< 15 headache days/month) and chronic migraine (\geq 15 headache days/month). Inclusion criteria were a) currently meeting International Classification of Headache Disorders (ICHD)-3 beta headache diagnosis for migraine using a semi-structured clinical interview and the validated American Migraine Study/American Migraine Prevalence and Prevention Study migraine diagnostic screener³⁶, b) self-reported and prospective diary-confirmed \geq 6 headache days per month, c) aged 18-65, d) ability to read English, and e) capacity to consent. Exclusion criteria were a) continuous headache over the course of 30 days, b) initiation of a preventative migraine treatment within four weeks of the baseline assessment or a plan to initiate preventive migraine treatment during the duration of the study, c) severe psychiatric illness that would interfere with participation in the treatment such as active suicidality, active psychosis, or failing a cognitive screen, or d) inability to adhere to headache diary during baseline period (recorded fewer than 26/30 days).

4) Participant Recruitment

Participants were recruited from neurology office referrals and local and online advertisements in the broader New York City area including New York, New Jersey and Connecticut. Participants were provided with the MBCT web page information, our team email and office phone number. All potential subjects were screened by study staff online or via a telephone call prior to the intake appointment.

5) Informed Consent

After screening, participants attended a baseline assessment visit where they will again be screened for eligibility. If eligible, participants were given the opportunity to provide written informed consent.

5) Procedure:

Those who consented to participation in this study completed a baseline assessment with a study coordinator. At the baseline assessment, participants completed a self-report questionnaire for demographic information and symptom severity, and completed baseline psychosocial surveys using the REDCap electronic data capture system, a secure data capture program available through Albert Einstein College of Medicine. Participants were given access to the REDCap Headache Diary Application for the duration of the four-week baseline assessment. If the participant did not have an iPhone or iPod touch, an iPod Touch was provided. The study coordinator provided education and orientation to the use of the headache diary application as well as the reminder system that will guide participants to optimal completion. At the conclusion of the 4-week baseline assessment period, all participants will complete psychosocial measures again via REDcap through an

email reminder.

Study participants received up to \$70 for participating in the study.

Participants who continue to meet study inclusion/exclusion criteria will be randomized to either the MBCT-M or WL/TAU group. We will use a randomization procedure stratified by episodic vs. chronic migraine based on headache days/month recorded in the daily headache diary. A statistician otherwise unrelated to the study used a computerized random number generator to randomize participants in random blocks of 2, 4, and 6 participants stratified by headache days/month (cut off score of 15).

During the 8-week treatment phase, participants randomized to the MBCT-M intervention group attended 8 weekly individual 75-90 minute sessions using a treatment protocol adapted from the MBCT for Chronic Headache Pain manual by [name]., and [name]. Each session included education, cognitive exercises designed to demonstrate how to think mindfully, and in-vivo mindfulness meditation practice designed to help participants systematically gain mindfulness skills throughout the course of treatment. Participants were given “homework,” including formal mindfulness meditation and informal mindful awareness exercises, labeling thoughts, identifying warning signs for stress and migraine, and planning nourishing activities, in between sessions. Homework was assigned each week, and participants were expected to develop a daily formal mindfulness practice (body scan meditation, seated meditation, breathing meditation). Participants were provided with a course manual, reading materials, and audio recordings to facilitate meditation practice. The weekly sessions were conducted by a clinical psychology student who had completed his or her master’s level training in the clinical psychology, health emphasis Ph.D. program at Ferkauf Graduate School of Psychology. All therapists completed training conducted by [name], who developed the MBCT for Chronic Headache Pain manualized treatment. The doctoral level students received clinical supervision from licensed and credentialed clinical psychologists. During the eight weeks of intervention, participants randomized to the MBCT intervention group continued to complete daily headache diary and record daily formal mindfulness practice for eight weeks. All sessions were audio-recorded and coded for treatment fidelity by two independent raters. Participants randomized to the WL/TAU group did not take the headache diary for the 8 week treatment period.

At the conclusion of the 8-week treatment period, all participants (in both the MBCT-M group and the WL/TAU group) completed headache diaries for 4 weeks. At the conclusion of the four weeks, participants completed one final set of psychosocial measures through the REDCap electronic data capture system. At this point, participants in the WL/TAU group were offered participation in MBCT-M.

Participants randomized to the MBCT group were asked to complete the psychosocial measures 6 months after completion of MBCT through the REDCap electronic data capture system.

Measures

Measures include the following:

Baseline Survey

We will ask demographics questions pertaining to age, gender, race and ethnicity, as well as validated questions about headache symptoms (AMPP diagnostic module). The latter will help investigators determine an International Classification of Headache Disorders – 3 beta headache diagnosis for each participant.

Headache Diary

Via the iPod Touch/Diary REDCap application, a daily headache diary will assess:

- Headache Day: Number of days on which headache was reported in a month.

- Headache Severity: Day-level headache severity with response options including 0 (None), 1 (Mild), 2 (Moderate), 3 (Severe). Average headache severity will be aggregated by month.
- Migraine Disability Index: (MIDI) a four-item scale that assesses disability related to four domains (Family and Home, Recreation, Social Activity, Job/Occupation). For each domain, an 11-point Likert scale allows for possible ratings of 0 (not at all) to 10 (totally). The four ratings are averaged; the final score is in the 0-10 range with higher scores indicating higher disability. Average day-level migraine disability (MIDI) score will be aggregated by month.

Psychosocial Surveys

- The Migraine Disability Assessment (MIDAS; primary outcome) is a 5-item, self-report instrument measuring disruption experienced due to migraine. Items target role functioning and ask about lost days of house-work, job-work, and non-work activities. Each item is an open question, allowing entry of number of days lost over 90 days. Total scores range from 0-450, and are categorized as <21 (Low Disability) and ≥21 (Severe Disability).
- The Headache-Related Disability Index (HDI; primary outcome) is a 25-item, self-report questionnaire of the emotional and functional impact of headache on daily activities. The items require a “yes,” “no,” or “sometimes,” response to assess participants’ perceived headache-related disability. Total scores range from 0-100; higher scores indicate higher disability.
- The Pain Catastrophizing Scale (PCS) is a 13-item self-report measure that conveys a participant’s level of pain-related, catastrophic thinking during painful experiences. The measure has three subscales: Rumination (4 items), Magnification (3 items) and Helplessness (6 items). Ratings are made on a 5-point scale from 0 (not at all) to 4 (all the time). Total scores range from 0 to 52; higher scores indicate higher catastrophizing.
- The Chronic Pain Acceptance Questionnaire (CPAQ) is a 20-item, self-report measure of pain-related acceptance, developed among chronic pain populations. Each item is rated on a Likert scale ranging from 0-7, with total scores ranging from 0-140, with higher scores indicating higher levels of acceptance.
- The Headache Specific Locus of Control (HSLC) is a 33-item measure designed to assess the extent to which individuals with recurrent headaches expect that the occurrence, worsening, and improvement of their headaches are influenced primarily by their own behavior (Internal), by chance or fate (Chance), or by the actions of medical professionals (Medical Professionals). Items are coded on a 5-point Likert-type scale ranging from 1 (strongly agree) to 5 (strongly disagree); total HSLC ranges from 33-165, with higher scores indicating more external locus of control.
- The Five Facet Mindfulness Questionnaire (FFMQ) is a 39-item self-report instrument containing five subscales: observing, describing, acting with awareness, non-judging of inner experience, and non-reactivity to inner experience. Each item has a 5-point response scale ranging from 1 (never or very rarely true) to 5 (very often or always true). Total scores range from 39-195 with higher scores indicating higher levels of mindfulness.
- The Headache Management Self-efficacy Scale (HMSE) is 25-item self report scale designed to capture the confidence a patient believes they have in their own abilities to prevent headache episodes and manage their pain. Each item is rated on a Likert scale ranging from 1-7, ranging from 1 (strong disagree) to 7 (strongly agree). Total scores range from 25 to 175 with higher scores indicating a higher degree of self-efficacy.
- The NIH PROMIS depression Short Form is an 8-item self-report measure developed by the National Institutes of Health that assesses emotional distress “in the past 7 days,” focusing on negative mood and negative self-views. Ratings are made on a 6-point scale, from 1 (Never) to 5 (Always). Scores are calibrated to a T score metric (M = 50, SD = 10) normed to U.S. population demographic means. Higher scores represent more severe depressive symptomology.
- The NIH PROMIS Anxiety Short Form is an 8-item self-report measure developed by the National Institutes of Health that assesses emotional distress “in the past 7 days,” focusing on fear, worry and hyper-arousal. Ratings are made on a 6-point scale, from 1 (Never) to 5 (Always).

Scores are calibrated to a T score metric ($M = 50$, $SD = 10$) normed to U.S. population demographic means. Higher scores represent more severe anxiety symptoms.

6) Data Analysis

Distributions of all study variables were evaluated for normality, skewness and kurtosis. Day-level imputation was used to impute missing diary data points (15.5%) for headache diary measures. Variables at baseline were described using mean and standard deviation for normally distributed variables, and number and percent for nominal variables. Differences between treatment groups for primary and secondary outcomes at baseline were evaluated using t-tests and chi-squares.

Intent-to-treat analysis used linear (continuous variables) and logistic (dichotomous variables) mixed models for repeated measures to estimate missing values and evaluate changes in outcomes. For survey variables, time was a 4-level variable (Month 0, 1, 2, and 4); for diary data, time was a two-level variable (baseline monitoring period vs. post-treatment evaluation period). Fixed effects were group, time, and their interaction. A significant interaction indicated the slope of the MBCT-M group differed from the slope of the WL/TAU group. Random effects were intercept and time. Akaike's information criterion indicated a first-order autoregressive covariance structure was appropriate for modeling month.

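### The analysis fits both primary survey outcomes at Months 0, 1, 2 and 4, but the procedures describe surveys in both arms only at Months 0, 1 and 4

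*Combined protocol and SAP*

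**What the plan says.** Section 6, Data Analysis, describes linear and logistic mixed models for repeated measures. For surveys it says "For survey variables, time was a 4-level variable (Month 0, 1, 2, and 4", and for the model, "Fixed effects were group, time, and their interaction". It reads a significant interaction as showing that the two arms' slopes differ.

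Both primary outcomes fall under this rule, because the Measures list places them among the psychosocial surveys: "The Migraine Disability Assessment (MIDAS; primary outcome) is a 5-item, self-report instrument measuring disruption experienced due to migraine" and "The Headache-Related Disability Index (HDI; primary outcome) is a 25-item, self-report questionnaire".

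The Procedure section (the second section numbered 5) gives these survey occasions:

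- At the baseline visit, participants "completed baseline psychosocial surveys using the REDCap electronic data capture system".
- "At the conclusion of the 4-week baseline assessment period, all participants will complete psychosocial measures again via REDcap". Randomisation is described after this step.
- After 8 weeks of treatment or waiting, both arms keep a diary for 4 weeks. Then: "At the conclusion of the four weeks, participants completed one final set of psychosocial measures".
- The MBCT-M arm alone is surveyed again 6 months after treatment.

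For the 8-week treatment phase, the section mentions a diary and a practice record in MBCT-M and no diary in WL/TAU. It names no survey in either arm. Section 2, Study Design, agrees, "with follow-up assessments at 1 and 6 months post-treatment", with the later one for the treatment group only.

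**The concern.** The levels of the time factor define the test on which the plan rests its claim of a group difference. If a reader cannot tell which surveys enter the model, the test for both primary outcomes is not fully specified.

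Timing also affects what a survey measures. MIDAS asks about 90 days. If randomisation is at week 4, a MIDAS at week 8 would cover 28 days after randomisation and 90 − 28 = 62 days before it. That is a different quantity from a post-treatment score.

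A second weakness lies in the test itself. Months 0 and 1 both precede randomisation. An overall interaction test spends a degree of freedom on the Month 0 to Month 1 comparison, where treatment can have no effect, and a chance difference there can contribute to a significant result.

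**Working it through.** **1. Survey calendar.** The inputs are a 4-week baseline, 8 weeks of treatment and a 4-week post-treatment diary, all from the Procedure section. Shared surveys fall at weeks 0, 4 and 4 + 8 + 4 = 16. Treatment ends at week 12. The plan does not define the origin of its months, so three were tried, in 4-week months:

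| Origin | Shared surveys | End of treatment | MBCT-M-only survey |
|---|---|---|---|
| Baseline visit | 0, 1, 4 | 3 | about 9 |
| Randomisation | −1, 0, 3 | 2 | about 8 |
| End of treatment | −3, −2, 1 | 0 | 6 |

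Only the first origin matches three of the plan's four levels. Month 2 is then week 8, halfway through treatment. Calendar months from the baseline visit give 0, 0.92 and 3.68, which adds no fourth time. The MBCT-M-only survey cannot be the missing level.

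**2. What can be estimated.** Arm sizes are 31 and 29 (section 3), total 60. With categorical time, the fixed effects have 1 (intercept) + 1 (group) + 3 (time) + 3 (interaction) = 8 columns.

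- Surveys at 0, 1, 2 and 4 in both arms: 60 × 4 = 240 planned records, rank 8, interaction df (2 − 1)(4 − 1) = 3.
- Surveys at 0, 1 and 4 only: 60 × 3 = 180 records in 2 × 3 = 6 arm-by-time cells, so rank 6. The Month 2 effect and its interaction with group drop out, and the interaction df is (2 − 1)(3 − 1) = 2.
- Month 9 in MBCT-M as the fourth level: 180 + 31 = 211 records, rank 7. The main effects take 5, leaving 2 interaction df.

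**3. Power of the tests.** The plan states no alpha, effect size, SD or correlation, so this is an illustration under assumptions: 5% two-sided alpha, complete data, chi-square approximation, and an effect confined to Month 4. Correlation is either compound symmetry or AR(1) spaced in months, with ρ from 0.3 to 0.8.

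Let d be the vector of between-arm differences, V the correlation matrix and C the contrasts of each later time with Month 0. The joint test has noncentrality proportional to (Cd)′(CVC′)⁻¹(Cd). A single contrast w has (w′d)²/(w′Vw). Here w is Month 4 minus the average of Months 0 and 1.

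The effect is scaled so that the three-level joint noncentrality is (1.960 + 0.842)² = 7.85.

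- Three-level joint test, 2 df: 70.9%.
- Single contrast, compound symmetry: w′Vw = 1.5(1 − ρ), and its noncentrality equals the joint value, 7.85. With 1 df, power is 80.0%.
- Single contrast, AR(1): w′Vw = 1.5 + ρ/2 − ρ³ − ρ⁴. Its noncentrality is nearly equal to the joint value at ρ = 0.3 (80.0%) and 0.973 of it at ρ = 0.8, that is 7.64 (78.9%).
- Four-level joint test, 3 df, compound symmetry: Month 2 acts as a third comparison measurement, so the variance falls from 3/2 to 4/3 of (1 − ρ). Noncentrality rises by 1.5 ÷ 1.333 = 1.125, to 8.83, and power is 70.2%.
- Four-level joint test, AR(1): 72–79%.
- Four-level joint test, half the effect already present at Month 2: 66–69% across both structures.

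**The case against.** The strongest reply is that Data Analysis reports finished work. It is in the past tense, gives the proportion of missing diary data as 15.5% and says that Akaike's criterion chose the covariance structure. A Month 2 survey may well have been given and left out of a short narrative procedure. The section names no survey during treatment, but it does not say that there was none. This stands, and it limits the point to a contradiction between sections.

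A reader might go further in three ways that the documents do not support.

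- **That the four-level test cannot be run.** This follows only if the procedures list every survey, which is not established. A three-level model can be fitted in any case.
- **That Month 2 was surveyed in one arm only.** Nothing says so, and the one survey described as arm-specific, at 6 months, is labelled as such.
- **That adding Month 2 cuts power from about 71% to about 65%.** The 64.5% figure holds noncentrality at 7.85 while moving to 3 df. In the same scenario the extra survey raises noncentrality, and power is 70% under compound symmetry and 72–79% under AR(1).

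It is also fair to say that the plan's wording about slopes leaves room for a linear-trend test with 1 df. The description of time as a four-level variable points to a categorical factor, but no test df is stated. Finally, a Month 2 survey taken in both arms would inform the trajectory and the handling of missing Month 4 values, so there is no good case for removing it from the model.

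**Conclusion.** The contradiction is real and concerns both primary outcomes: four time levels in the analysis, three shared surveys in the procedures, and no choice of origin that reconciles them. If the procedures are complete, the interaction test has 2 df instead of 3. If a Month 2 survey was given in both arms, the model has full rank and the omission lies in the procedures. The documents cannot show which is true.

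Whichever holds, the Month 4 contrast answers the efficacy question more directly than an overall interaction. Under the stated assumptions its power is about 79–80% against about 71% for the three-level joint test, a gain of 8 to 9 points. Against a four-level joint test the gain depends on the correlation: about 10 points under compound symmetry, and none under AR(1) at ρ = 0.8. These figures illustrate the comparison and are not the trial's actual power. The plan's model, with random intercept and time and an autoregressive structure, could shift them.

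**What to change.** - Reconcile Procedure with Data Analysis and define the origin of the months. Either restate the survey time factor as Months 0, 1 and 4 or, if a Month 2 survey was given, add it to Procedure with its arms, timing and instruments, and keep it in the model.
- From the same mixed model, base the efficacy conclusion for MIDAS and HDI on the between-arm difference in change from the average of the two pre-randomisation surveys to Month 4, a 1-df contrast, instead of on any significant group-by-time interaction.
- Because the analysis appears already to have been run, report this contrast beside the interaction test and label it as added afterwards.

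The cost is wording in two sections and one extra contrast, with a refit if the time factor changes. The downside is that a contrast added after the analysis carries less confirmatory weight, and the report must say so.

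### Randomisation was stratified at 15 headache days/month, but the mixed models leave the stratum out, so reported standard errors are too large where stratum predicts change, chiefly for diary headache days

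*Combined protocol and SAP*

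**What the plan says.** Section 3) Study Population states "Recruitment and randomization was stratified by episodic migraine" and chronic migraine, with the boundary at 15 headache days/month. Section 5) Procedure gives the source of the stratum: "We will use a randomization procedure stratified by episodic vs. chronic migraine based on headache days/month recorded in the daily headache diary". The same section specifies random blocks of 2, 4 and 6 within stratum. Thirty-one participants went to MBCT-M and 29 to WL/TAU.

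The Headache Diary part of Measures defines the headache-day outcome as "Number of days on which headache was reported in a month". MIDAS and HDI are the primary outcomes, and MIDAS is built from lost days, each item "allowing entry of number of days lost over 90 days".

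Section 6) Data Analysis describes the mixed models: "Fixed effects were group, time, and their interaction". Random effects are intercept and time. The treatment effect is read from the interaction: "A significant interaction indicated the slope of the MBCT-M group differed from the slope of the WL/TAU group". Survey outcomes have four time levels, and diary outcomes have two, baseline and post-treatment. No stratum term, baseline headache-day covariate or stratified sensitivity analysis appears anywhere in the document.

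**The concern.** Blocking within strata makes the arms nearly equal in their episodic/chronic mix, so chance imbalance in that mix adds almost nothing to the sampling variation of the treatment contrast. A model without the stratum does not know this. It leaves the between-stratum variation in its residual and reports a standard error larger than the true sampling SD.

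This does not affect every outcome. The interaction compares changes, so a constant difference between chronic and episodic participants drops out. What matters is whether the strata change by different amounts.

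For diary headache days they should. The stratum is the baseline-period count cut at 15, and that count is also the first time level of the outcome. Participants selected above 15 will on average drift down, and those below will drift up, in both arms. For MIDAS a link is plausible because it counts lost days. For HDI the document offers no reason to expect one.

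At stake are confidence intervals wider than the design warrants and a conservative test, in a trial of only 60.

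**Working it through.** The document states no alpha, power, SD or correlation, so there is no planned figure to reproduce. From the document come 31 and 29 participants, the cut at 15 days, blocks of 2/4/6, eligibility from 6 headache days and two diary time levels. Two-sided 5% testing, 80% power and the quantities below are assumptions.

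**Step 1: general effect.** With two time points and complete data, group-by-time equals the difference in mean change. Let R² be the share of variance in change explained by stratum.

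- SE ratio (adjusted/unadjusted) = √(1−R²)
- True size of the unadjusted nominal 5% test under stratified blocks = 2[1−Φ(1.96/√(1−R²))]
- Unadjusted power under stratified blocks = Φ(0.8416/√(1−R²)), where 80% is the power computed ignoring stratification
- Adjusted power from the noncentral t with 57 df, 31 versus 29 and d = 0.736 (80% at 58 df)

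| R² | SE ratio | Unadjusted size | Unadjusted power | Adjusted power | Net gain (points) |
|---|---|---|---|---|---|
| 0% | 1.00 | 5.0% | 80.0% | 80% | about 0 |
| 5% | 0.975 | 4.4% | 80.6% | 82% | about 1 |
| 10% | 0.949 | 3.9% | 81.3% | 84% | about 3 |
| 20% | 0.894 | 2.8% | 82.7% | 88% | about 5 |

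**Step 2: R² for diary headache days.** Take baseline and post-treatment counts as bivariate normal with equal variances, correlation ρ and chronic share p. Then R² = [(1−ρ)/2] × φ(z)²/[p(1−p)], where z is the normal quantile at p. The second factor is 0.637 at p = 0.5 and 0.576 at p = 0.3 or 0.7.

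| ρ | R², p = 0.5 | R², p = 0.3 or 0.7 |
|---|---|---|
| 0.3 | 0.223 | 0.201 |
| 0.5 | 0.159 | 0.144 |
| 0.7 | 0.095 | 0.086 |
| 0.9 | 0.032 | 0.029 |

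For example, at ρ = 0.5 and p = 0.5: 0.25 × 0.637 = 0.159. The extremes give SE ratios of √(1−0.029) = 0.99 and √(1−0.223) = 0.88.

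**Step 3: simulation with N = 60 and stratified blocks of 2/4/6.**

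- Baseline mean 15, SD 5, truncated at 6 days or more, ρ = 0.5 (5,000 trials): R² was 0.138. The unadjusted model SE was 0.252 against a true SD of 0.234. Size was 3.6% unadjusted and 5.0% adjusted; power was 81.3% and 85.9%. The SE ratio was 0.926.
- Baseline mean 14, SD 6, truncated to 6–27 days (4,000 trials per setting): at ρ = 0.5, 0.7 and 0.8, size was 3.8%, 4.3% and 4.6% unadjusted and 5.1%, 5.2% and 5.1% adjusted. Power went from 80.0% to 83.9%, 75.3% to 78.1% and 75.3% to 76.6%.
- Outcome whose change is unrelated to stratum: SE ratio 1.000, so neither loss nor gain.

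**Step 4: which term does the work.** In one simulated complete data set, adding only a stratum main effect left the group-by-time estimate (0.0204) and its SE (1.6604) unchanged. Only stratum-by-time can remove variation in change.

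**The case against.** The case against is that this is a minor efficiency point.

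- **No harm is shown for a primary outcome.** This stands. The mechanism follows from the trial's definitions only for diary headache days. For MIDAS it is a possibility, and for HDI there is no basis.
- **The true precision is already there.** This also stands, and it sharpens the point. In the second simulation at ρ = 0.5 the true sampling SD was 0.228 with or without the stratum, while the reported SE was 0.245 without it and 0.229 with it. Adjustment corrects the reported uncertainty; it hardly moves the estimator. The planned analysis is conservative, and a significant result under it is not undermined.
- **The size rests on assumptions.** True. If the post-treatment SD is k times the baseline SD, the first factor of R² becomes (ρk−1)²/(1+k²−2ρk). At ρ = 0.9 and p = 0.5, k = 1.1 gives (0.0001/0.23) × 0.637, near zero, while k = 0.9 gives (0.0361/0.19) × 0.637 = 0.12. The calculation also assumes complete data and two time points. It therefore does not transfer directly to the four-level survey models or allow for the 15.5% of diary data points that were imputed.
- **Continuous baseline days would explain more.** Under Step 2 they explain (1−ρ)/2 of the variance in change, 25% at ρ = 0.5 against 16% for the stratum. That is a fair alternative for this outcome, but it does not make stratum-by-time unsound.
- **The analysis is written in the past tense.** So any added term is post hoc and must be labelled as such.

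These points limit the importance of the omission. None of them shows that leaving out the stratum was justified.

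**Conclusion.** The concern holds within a narrow scope. The listed fixed effects omit the factor used to randomise, and no reason is given. For diary headache days, under the assumed correlations of 0.3 to 0.9, chronic shares of 30% to 70% and equal variances, the adjusted SE would be 0.99 to 0.88 of the planned one. The simulated size of the planned test at correlations of 0.5 to 0.8 was 3.6% to 4.6% instead of 5%. The net power gain stays at about 5 points or less for R² up to 20%. The document does not quantify the loss for any outcome, and it is zero wherever stratum does not predict change. The omission creates no bias and no excess type I error in the complete-data setting examined. It should be corrected because correction is nearly free, but it does not invalidate the planned analysis.

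**What to change.** Add the randomisation stratum (episodic/chronic, as used at randomisation) and stratum-by-time as fixed effects in the linear mixed models, or state why the stratum is left out. A main effect alone is not enough, because it gives essentially no gain for group-by-time. If the data have already been analysed, show the result next to the original model and label it a revised or sensitivity analysis. Stratum may also enter the logistic models, but the odds ratio then becomes conditional on stratum and the SE gains above do not carry over.

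No new data are needed, since the stratum was fixed at randomisation for all 60 participants. The terms use one degree of freedom per modelled visit: four for survey outcomes and two for diary outcomes. If stratum turns out to be uninformative, the power cost in the two-time-point calculation is about 0.02 percentage points (57 versus 58 df). The real cost is re-running the models and reporting openly that the terms were added afterwards.

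### The survey model leaves the arms free to differ before randomisation, so MIDAS and HDI effects measured from Month 0 lose precision and over-correct for chance baseline imbalance

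*Combined protocol and SAP*

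**What the plan says.** Two survey scores are named as primary in Measures, Psychosocial Surveys: "The Migraine Disability Assessment (MIDAS; primary outcome) is a 5-item, self-report instrument" and "The Headache-Related Disability Index (HDI; primary outcome) is a 25-item, self-report questionnaire". In 6) Data Analysis the baseline survey is a row of the outcome: "For survey variables, time was a 4-level variable (Month 0, 1, 2, and 4"). The mean model is given in full: "Fixed effects were group, time, and their interaction". The effect is read from the interaction: "A significant interaction indicated the slope of the MBCT-M group differed from the slope of the WL/TAU group". No baseline covariate and no equal-baseline constraint is listed. Baseline differences are handled only by testing: "Differences between treatment groups for primary and secondary outcomes at baseline were evaluated using t-tests and chi-squares".

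On timing, 5) Procedure says: "Those who consented to participation in this study completed a baseline assessment with a study coordinator". It then describes a second set of psychosocial measures at the end of the four-week run-in, and randomisation after that. The allocation in 3) Study Population was "randomized 31 participants to MBCT-M and 29 to WL/TAU".

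**The concern.** Randomisation makes the expected Month 0 mean the same in both arms. A model with group, time and their interaction nevertheless fits a separate Month 0 mean per arm, and measures the effect as departure from it. Any chance difference at Month 0 is therefore subtracted in full from a later difference, although only a fraction equal to the baseline-to-follow-up correlation is expected to persist. This has two consequences:

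- The interval for the effect is wider than the data require.
- In a given trial the estimate is pushed in the direction opposite to the chance imbalance.

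The baseline t-tests do not help, because nothing in the model depends on their result. Randomisation was stratified on headache days, not on MIDAS or HDI. With 60 participants and two primary survey outcomes, discarding baseline information matters more than it would in a large trial.

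**Working it through.** The documents contain no sample-size or power calculation, so there is no planned figure to reproduce.

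**Inputs from the documents.** 31 and 29 participants; surveys at Months 0, 1, 2 and 4; fixed effects as quoted.

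**Assumptions, because the documents give no figure.** Compound symmetry with correlation ρ from 0.4 to 0.9, equal SD at each visit, two-sided 5% level, complete data unless stated, correlations treated as known. Results are in SD units.

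**Step 1: what the model estimates.** With time as a factor and complete data, the fitted means are the observed arm-by-visit means whatever the covariance structure. The Month 4 minus Month 0 interaction is therefore the raw difference in mean change.

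**Step 2: variances.** Let k = 1/31 + 1/29 = 0.06674.

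- As written: 2(1 − ρ)k. At ρ = 0.5 this is 0.06674, SE 0.258.
- Common Month 0 mean: (1 − ρ²)k. At ρ = 0.5 this is 0.05006, SE 0.224.
- Ratio: 2/(1 + ρ).
- Common means at Months 0 and 1 (if both precede randomisation): (1 − 2ρ²/(1 + ρ))k. At ρ = 0.5 this is 0.04449, a ratio of 0.06674/0.04449 = 1.50.

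| ρ | As written ÷ common Month 0 | As written ÷ common Months 0 and 1 |
|---|---|---|
| 0.4 | 1.43 | 1.56 |
| 0.5 | 1.33 | 1.50 |
| 0.6 | 1.25 | 1.45 |
| 0.7 | 1.18 | 1.42 |
| 0.8 | 1.11 | 1.38 |
| 0.9 | 1.05 | 1.36 |

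Generalised least squares on the four visits reproduces these values. With 20% dropout the first ratio is about 1.27 at ρ = 0.5 and 1.15 at 0.7. If time is instead read as a linear slope, it is 1.28 and 1.14 with complete data.

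**Step 3: sensitivity to imbalance.** The SE of a chance baseline difference is √k = 0.258 SD. Given a one-SE imbalance, the change-score estimate moves by (1 − ρ) × 0.258 in the opposite direction: 0.155 SD at ρ = 0.4, 0.129 at 0.5, 0.078 at 0.7 and 0.026 at 0.9. Averaged over randomisations the shift is zero.

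**Step 4: the overall interaction.** With time as a four-level factor, the interaction has 3 df. Take illustrative effects of 0, 0, 0.6 and 0.6 SD at Months 0, 1, 2 and 4, and ρ = 0.5.

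- As written: the sum of squares of the effects about their mean is 0.36, so the noncentrality is 0.36/(0.5 × 0.06674) = 10.8. Power is 80%.
- Common Month 0 mean: the noncentrality is (2 × 0.72 − 0.4 × 1.44)/0.06674 = 0.864/0.06674 = 12.9. Power is 87%.
- At ρ = 0.7 the two powers are 96% and 97%.

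**Step 5: other contrasts.** For Month 4 minus Month 1 under compound symmetry, constraining Month 0 alone gives a ratio of 1.00. Constraining Months 0 and 1 gives 1.50 at ρ = 0.5. The unconstrained contrast of Month 4 minus the mean of Months 0 and 1 has variance 1.5(1 − ρ)k = 0.05006 at ρ = 0.5, the same as the common-Month-0 result. Which pre-randomisation visits are constrained therefore matters.

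**The case against.** The written analysis is standard and valid, so this could be called a preference. That is right as to validity: the estimate is unbiased over randomisations and the test is sound. A reader might infer a biased or invalid primary test, but the documents do not support that.

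A reader might also infer that the loss applies to any Month 4 comparison. It does not, as steps 4 and 5 show. The plan names no single contrast, and its reference to slopes sits awkwardly with a four-level factor. For the Month 4 minus Month 0 contrast alone, power for 0.6 SD at ρ = 0.5 would be 64% against 76%. That figure should not be presented as the trial's power.

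It is tempting to add that the baseline t-tests have low power to detect an imbalance. That argument fails: power refers to a true population difference, which randomisation rules out. The sound point is only that the model does not act on the tests.

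Three further qualifications stand:

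- MIDAS is also categorised at 21, and dichotomous outcomes go to logistic models. The documents do not say which form is primary. The variances above apply only to the continuous score.
- Stratifying on headache days probably limits imbalance somewhat, and step 3 gives no credit for this.
- At a correlation of 0.8 or more, the gain from constraining Month 0 alone is small. Estimating the adjustment costs about 2% of variance (1 + 1/56), which takes back part of it.

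None of this removes the loss for effects measured from Month 0, or supplies a reason to fit separate arm means before randomisation.

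**Conclusion.** The point holds as a matter of precision. For MIDAS and HDI as continuous scores, the Month 4 minus Month 0 effect has 43% to 5% more variance than with a common Month 0 mean, for assumed correlations of 0.4 to 0.9 under compound symmetry. It also over-corrects for whatever imbalance chance produced. The exact identity with raw change rests on complete data and time as a factor; with dropout or a linear slope it is approximate, and the loss remains. The benefit to the overall interaction test is smaller.

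The full gain depends on where Month 1 falls. Four weeks of run-in, eight of treatment and four of follow-up make 16 weeks, which fits Month 4 if Month 0 is the intake visit. Month 1 would then be the end-of-run-in survey, also before randomisation. This is an inference, since the documents do not map months to visits.

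**What to change.** 1. State which surveys precede randomisation. Fit the same mixed model with one common mean for both arms at each of them: Month 0, and Month 1 if it is the end-of-run-in survey. Keep time, and keep group-by-time only for later visits.
2. Alternatively, enter the pre-randomisation score or scores as covariates with covariate-by-time terms. The two routes need not agree exactly when data are missing.
3. Report arm differences at post-randomisation visits only.
4. Describe baseline values by arm without significance tests.

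The cost is a change to the model statement and a re-run on data already held, with fewer parameters under the first route. Randomisation justifies the common-mean assumption. However, 6) Data Analysis is written in the past tense and reports an observed missing-data rate and a covariance structure already chosen. If results are already known, the constrained model should be labelled a sensitivity analysis beside the written one, not substituted for it.
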